**vi. Sample size calculation**

Based on our clinical experience with low dose US-ISB (ropivacaine 0.5% 5ml) as well as previously published work, we expect mean sensory block duration of 12 hours with a standard deviation of 4 hours.

Based on the literature, we expect a mean prolongation of block time associated with perineural dexamethasone to be approximately 50% thereby increasing block duration to 18 hours. Defining an equivalency margin of 2 hours, we estimate that 87 patients per group (174 total) will be required to reliably test our hypothesis given  $\alpha=0.05$  and  $\beta=0.9$ . To account for incomplete data or loss to follow-up, the plan is to recruit 90 patients per group (180 total).

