**B. Hypothesis**

Perineural dexamethasone added to the local anesthetic ropivacaine for low dose, ultrasound guided interscalene brachial plexus block (US-ISB) provides similar duration analgesia to that of US-ISB with local anesthetic alone and intravenous dexamethasone.

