There are several reasons that warrant a new randomized trial. Chiefly, all of the previous trials do not reflect modern regional anesthetic practice. These trials utilized peripheral nerve stimulation (PNS) and local anesthetic volumes of 30 to 40 ml. Modern ultrasound guided ISB (US-ISB) allows for more accurate, targeted deposition of local anesthetic with volumes ranging from 5 to 10 ml with no difference in block efficacy or duration compared to larger volumes ( $\geq 20$ ml). Despite this, critics of low volume US-ISB persist with the belief that low-volume techniques, with their reduced local anesthetic dose, inherently produce a shorter duration block of lesser quality compared to higher volume. However by advocating for higher volume ISB, practitioners guarantee diaphragmatic dysfunction from ipsilateral phrenic nerve block (near 100% with volume  $\geq 10$ ml). An ideal solution would be a local anesthetic with adjuvant mixture that allowed administration of lower volumes but with prolonged analgesic duration. The use of low dose local anesthetic with dexamethasone could be one such solution. A trial that demonstrates enhanced block quality and duration associated with perineural dexamethasone added to low dose local anesthetic may allow us to achieve both prolonged duration of effect and reduced side effects due to unwanted local anesthetic spread. This would create further significant benefits for patients and further promote the use of low dose local anesthetic techniques to anesthesiologists who do not currently use this technique.

Secondly, there is some data to suggest that systemic dexamethasone may also prolong block duration.

The most recent trial failed to show a difference in block duration between systemic and perineural dexamethasone. The conclusions of this trial were that the two modes of administration were equivalent

at prolonging block duration. This was methodologically incorrect, as the trial was not specifically designed as an equivalency trial with defined equivalency margins.

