The ISB will be performed using a 13-6 MHz 38-mm linear US probe with appropriate sterile barrier (M-Turbo®; SonoSite Inc., Bothell, WA) at the C6 nerve root level via posterior approach with a 22-gauge insulated 50-mm regional block needle (Stimuplex®; B.Braun Medical, Bethlehem, PA). After satisfactory position of the needle tip is achieved and visualized, the injectate will be administered slowly. The total volume injected is 6 ml to allow for the 1 ml of dead space in the block needle line and needle itself.

Control	Experimental
Ropivacaine 1% 3.5 ml + 0.9% saline 3.5 ml, total volume 7.0ml, final concentration 0.5% ropivacaine Intravenous infusion D5W with dexamethasone 4mg, 50 ml to be infused over 15 minutes	Ropivacaine 1% 3.5 ml + 0.9% saline 2.5 ml, 0.4% dexamethasone 1.0 ml, total volume 7.0 ml, final concentration 0.5% ropivacaine, dexamethasone 4mg Intravenous infusion D5W, 50ml

Dexamethasone has been sourced from Sandoz which contains sodium bisulfite, but not the preservative benzyl alcohol which is present in other preparations. The local anesthetic injectate will be prepared in a blinded syringe by trained block room nurses that are aware of group allocation but will take no further part in study procedures or assessments. This individual will prepare the injectate in a 10ml syringe labelled as followed 'ropivacaine 0.5% +/- dexamethasone 4mg' as well as the intravenous infusion labelled 'saline placebo or dexamethasone 4mg'. All other personnel - patients, anesthesiologists performing the ISB or caring for the patient in the operating theatre, anesthesia assistants, surgeons, research assistants performing outcome measures, and statisticians - will remain blinded.

**The following two paragraphs outline standard of care practice (unless otherwise stated) for patients undergoing arthroscopic shoulder surgery at HoAC:**

Patients will undergo general anesthesia with a standardized induction technique using fentanyl 1 - 4mcg/kg, and propofol 1-3mg /kg both at the discretion of the attending anesthesiologist and titrate to effect. Endotracheal intubation will be facilitated with rocuronium 0.6-1.0mg/kg if necessary or a

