**vii. Statistical analysis**

Demographic data will be summarized and expressed using appropriate measures of central tendency and dispersion for continuous data, means and standard deviations will be provided (medians and interquartile ranges for non-normally distributed data) and for categorical data counts and percentages will be displayed. The primary outcome, time to first sensation of pain at the surgical site, will be compared between the two groups using a two sample equivalence test of means. Secondary outcomes that are time based will also be assessed in the above manner (time to first analgesic request, duration of motor block). Continuous secondary outcomes (opioid consumption, NRS) will be assessed with repeated measures ANOVA while blood glucose will be assessed with the t-test. Categorical outcomes (paresthesia,

infection, nausea) will be compared with the Chi square or Fisher's exact test for the case of low expected cell counts.

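### Does leaving out the side of alpha and the confidence level leave the primary equivalence rule open?

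*Combined protocol and SAP*

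**What the plan says.** Section E.vi (Sample size calculation) starts from a low-dose ropivacaine block: "we expect mean sensory block duration of 12 hours with a standard deviation of 4 hours". It expects perineural dexamethasone to lengthen the block by "approximately 50% thereby increasing block duration to 18 hours". It then sets the margin, "Defining an equivalency margin of 2 hours", and concludes "we estimate that 87 patients per group (174 total) will be required to reliably test our hypothesis given" α = 0.05 and β = 0.9. Recruitment is raised to 90 per group for losses.

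Section E.vii (Statistical analysis) says that time to first pain "will be compared between the two groups using a two sample equivalence test of means". It does not repeat the margin or alpha, and it gives no confidence level and no criterion for declaring equivalence. The only other threshold is the interim p-value of 0.001 in section E.ix, which does not set the final rule.

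The hypothesis (section B) is that perineural dexamethasone "provides similar duration analgesia to that of US-ISB with local anesthetic alone and intravenous dexamethasone". The treatment table in section E.iii gives the control arm "Intravenous infusion D5W with dexamethasone 4mg, 50 ml to be infused over 15 minutes", so both arms receive dexamethasone.

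**The concern.** Equivalence is the purpose of this trial, and an alpha of 0.05 can be read in two ways in an equivalence setting. As the level of each of two one-sided tests, it means that the 90% confidence interval must lie within ±2 hours. As a two-sided level, it means the 95% interval must. The two readings can give opposite primary conclusions from the same data, and power differs between them by about 8 percentage points. The background section criticises a previous trial because "the trial was not specifically designed as an equivalency trial with defined equivalency margins", so a reader expects this plan to be exact about its own rule.

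Two smaller matters point the same way. A beta of 0.9, taken literally, means 10% power. And the 4-hour standard deviation is attached to a 12-hour ropivacaine block, although neither arm receives ropivacaine without dexamethasone.

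**Working it through.** **Inputs.** From section E.vi: margin 2 h, SD 4 h, α = 0.05, and β = 0.9 read as power 0.90. From section E.iii: 1:1 allocation. Assumed: a true difference of 0 h between the arms, since the hypothesis is similar duration and no other value is given for this contrast.

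**Reproducing the plan's figure** (normal approximation, two one-sided tests):

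n per group = 2 × (SD/margin)² × (z for 1−a + z for 1−β/2)², where a is the level of each one-sided test.

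- a = 0.05 (90% interval): 2 × (4/2)² × (1.645 + 1.645)² = 86.58, so **87**. This is the plan's number.
- a = 0.025 (95% interval): 2 × (4/2)² × (1.960 + 1.645)² = 103.96, so **104**. This is not the plan's number.

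The exact t-based calculation gives 88 and 105.

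**Other readings of the inputs.**

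| Reading | n per group |
|---|---|
| Equivalence, 90% interval, power 0.80 | 69 |
| Equivalence, 95% interval, power 0.80 | 85 |
| Superiority, 2 h difference, two-sided 0.05, power 0.90 | 85 |
| Non-inferiority, 2 h margin, one-sided 0.025, power 0.90 | 85 |
| Superiority, 6 h difference (12 to 18 h), two-sided 0.05, power 0.90 | 10 |
| Equivalence, β = 0.9 taken literally (power 0.10) | 26 (90% interval) or 35 (95% interval) |

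Three of these come close, at 85, but none gives 87 and none matches both the stated test and the stated power. The last row shows that β = 0.9 is a label for power 0.90.

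**What would turn on the choice** (exact t-based, SD 4 h). Half-width = t × 4 × √(2/n). With 87 per group:

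- 90% interval: half-width 1.003 h, so equivalence is declared up to an observed difference of 2 − 1.003 = 0.997 h.
- 95% interval: half-width 1.197 h, so up to 2 − 1.197 = 0.803 h.

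| | 90% interval | 95% interval |
|---|---|---|
| Power at true difference 0, 87 per group | 89.9% | 81.3% |
| Power at true difference 0, 90 per group | 91.0% | 83.1% |
| False equivalence at a true difference of 2 h | 5.0% | 2.5% |

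With 87 per group the two rules disagree with probability 8.6%, 11.2% and 12.8% at true differences of 0, 0.5 and 0.9 h.

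**Which rule has size 0.05?** Equivalence is declared only if both one-sided tests reject. At the margin the error rate is therefore that of one test, and alpha is not split. Two tests at 0.05 give a procedure of size 5.0%, the stated alpha; the 95% interval gives 2.5%. Any result that passes the 95% rule also passes the 90% rule, so even an analyst who chose between them after seeing the data could not exceed 5.0%.

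**The case for a change.** The strongest reply is that a rule recovered by working back from the sample size is not written down, and a sample size does not bind the analyst. One sentence would remove all doubt, and the time-based secondary outcomes go through the same test. It is true that no section states the side of alpha, the confidence level or the criterion. The probabilities of disagreement are also correct as arithmetic.

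They describe, however, an analyst who departs from the rule that the stated test, margin, alpha and sample size jointly imply. Such a departure would make the claim of equivalence harder to reach, at a cost in power; it would not raise the false-equivalence risk above the stated 5%. The background section's criticism of the previous trial concerns the lack of an equivalence design with defined margins. This trial has both.

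On the standard deviation, the plan does not say that 4 h is assumed to carry over to blocks with dexamethasone. The power does depend on it: with 90 per group and no true difference, 90% power holds up to an SD of 4.06 h. But section E.vi gives clinical experience and published work as its basis, nothing in the document points to a larger value, and the test would use the SD observed in the trial. A larger SD would cost power but would not make the conclusion invalid.

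**Conclusion.** No change is needed. The margin, the type of test, alpha and the sample size are all stated. The missing detail is the confidence level, and the standard reading of an equivalence test at alpha 0.05 supplies it: a 90% interval for the difference in means lying wholly within ±2 h. The plan's 87 per group agrees with that reading (86.58 before rounding) and not with a 95% interval (103.96). Followed as written, the analysis has a false-equivalence risk of 5.0% at the margin and power of 91.0% with 90 evaluable patients per group. The beta of 0.9 is a clerical slip for power of 0.90 and changes neither figure.

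This rests on an SD of 4 h in both arms, no true difference, and a symmetric margin. The first is the plan's own figure, the second follows from its hypothesis, and the third is the ordinary meaning of an equivalence margin.

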**vii. Statistical analysis**

Demographic data will be summarized and expressed using appropriate measures of central tendency and dispersion for continuous data, means and standard deviations will be provided (medians and interquartile ranges for non-normally distributed data) and for categorical data counts and percentages will be displayed. The primary outcome, time to first sensation of pain at the surgical site, will be compared between the two groups using a two sample equivalence test of means. Secondary outcomes that are time based will also be assessed in the above manner (time to first analgesic request, duration of motor block). Continuous secondary outcomes (opioid consumption, NRS) will be assessed with repeated measures ANOVA while blood glucose will be assessed with the t-test. Categorical outcomes (paresthesia,

infection, nausea) will be compared with the Chi square or Fisher's exact test for the case of low expected cell counts.

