**ii. Exclusion Criteria**

1. Lack of patient consent (including: inability to read or understand the ICF)
2. Allergy to dexamethasone or ropivacaine
3. BMI  $>$  35 kg/m^2

4. Contraindications to low dose dexamethasone including peptic ulcer disease, systemic infection, glaucoma, active varicella/herpetic infections, diabetes mellitus
5. Contraindications to ISB including severe Chronic Obstructive Pulmonary Disease (Forced expiratory volume < 40% predicted), coagulopathy, pre-existing neurologic deficit in ipsilateral upper extremity, localized infection
6. Pregnant or nursing females
7. Chronic opioid use defined as > 30mg oral morphine or equivalent per day
8. Unable to take acetaminophen or celecoxib

iii. **Protocol**

Patients scheduled for arthroscopic shoulder surgery will be approached for participation by research assistants in the pre-operative anesthetic clinic. Patients providing informed consent will be allocated 1:1 in blocks of 10 using a computer generated random number table (randomization will be stratified by site) and blinding of group allocation will be maintained with sequentially numbered, sealed, opaque envelopes.

**The following paragraph outlines standard of care practice (unless otherwise stated) for patients undergoing arthroscopic shoulder surgery at HoAC:**

On the day of surgery, patients will be pre-medicated with oral acetaminophen 1000mg, and oral celecoxib 400mg, unless otherwise stated by the attending physician. Once intravenous access is secure and standard monitors applied (electrocardiogram, non-invasive blood pressure cuff, continuous oxygen saturation), patients will receive sedation with intravenous midazolam (1-2mg). The lateral aspect of the neck including the supraclavicular fossa ipsilateral to the surgical site will be cleansed with standard isopropyl alcohol/chlorhexidine gluconate solution. The US-guided ISB will be performed under sterile conditions by a staff regional anesthesiologist, regional anesthesia fellow, or residents under supervision.

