**iv. Primary Outcome**

- Duration of sensory block – defined as time from end of injection to first sensation of pain at surgical site

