**viii. Trial conduct and Data collection/management**

The coordinating centre for this trial will be Sunnybrook Health Sciences Centre where the study coordinator and central data clerk will be based. A physician lead will be available at SHSC to answer patients' questions about the study as well as acting as a resource for the site specific study coordinator regarding patient eligibility and education of required hospital staff. The master randomization list will be kept at SHSC.

Data will be collected on a customized case report form (CRF) that includes all relevant demographic and intra-operative data as well as each outcome sought. Patients will be provided with a home diary to complete that will capture all outcomes sought that are not obtained in hospital. CRFs and home diaries will be completely de-identified with only patient study number, age (in years), and gender as identifiers. Data from the CRFs will be entered into a database at each site on secure, password protected computers with hospital network backup. The master file linking identifying data (name, MRN, date of birth) and study number will be kept in a separate file on a secure, password protected computer with hospital network backup.

CRFs will be divided into 2 categories: "CRFs" and "Source-CRFs". "Source-CRFs" are the documents used by the RA or patient to directly capture study data. They include: the pain diary, side effect questionnaires and the sensory and motor block assessments. "CRFs" will be completed with data transcribed from a source document. They include: Preoperative details, intra-operative data collection and medication administered in the Post Anesthesia Care Unit (PACU) and Day Surgical Unit (DSU) all obtained from medical records.

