#### **ix. Data safety monitoring plan**

This study involves the off-label use of dexamethasone. Consequently, an application to Health Canada will be made to obtain regulatory approval for the use of perineural dexamethasone. All adverse events will be documented (serious or not, related or not, expected or not) and reported following the Site

Guidance on Safety Reporting document. Serious adverse events are not expected. The severity of the adverse event will be coded as mild, moderate, or severe. The association with the intervention will be coded as unrelated, unlikely related, possibly related, probably related, or definitely related. The principal investigator will review all adverse events and act as safety monitor. These will be communicated to Health Canada and the Research Ethics Board of each respective institution. The independent reviewers will determine if the off-label use of dexamethasone contributed in any way to the adverse event and will make recommendations to either terminate, or modify study protocols.

The following are potential side effects often associated with surgical procedures that are not considered adverse events related to this study (obtained confirmation from five other physicians who declare no conflict of interest) and will therefore not need to be assessed and recorded by the QI in cases where these side effects are reported by study patients while they are in hospital and at home during post-operative follow-up telephone interviews:

- Headache/dizziness/nausea/vomiting/wheezing
- Bruising in the arm
- Gritty feeling in the eye/blurred vision/mild visual disturbance
- Bradycardia/tachycardia
- Complications associated with general anesthesia such as major cardiac events
- Local anesthetic toxicity
- Hemidiaphragmatic paresis (temporary)
- Hoarse voice (temporary)
- Horner's syndrome (temporary)
- Pruritus
- Changes in blood pressure
- Oxygen saturation below 90%
- Pain, cellulitis, or muscle spasm in areas other than the nerve block injection

A single interim analysis will be performed at 50% enrolment. If the data analysis indicates equipoise no longer exists, the study will be stopped early. The Haybittle-Peto threshold will be utilized (p=0.001).

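### Randomisation is stratified by site but the primary equivalence test has no site term; if sites differ, the test is conservative and some precision is given up

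*Combined protocol and SAP*

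**What the plan says.** Section E.iii (Protocol) has patients "allocated 1:1 in blocks of 10 using a computer generated random number table" and adds that "randomization will be stratified by site".

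The trial has more than one site. Section E.viii says "Data from the CRFs will be entered into a database at each site", and section E.ix refers to the "Research Ethics Board of each respective institution". Neither the number of sites nor their expected sizes are given.

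The primary outcome (E.iv) is a duration, "defined as time from end of injection to first sensation of pain at surgical site". Under E.vii it "will be compared between the two groups using a two sample equivalence test of means", and the time-based secondary outcomes are handled in the same way. No section plans a site term, a stratified analysis or any other covariate adjustment.

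For the sample size (E.vi), "we expect mean sensory block duration of 12 hours with a standard deviation of 4 hours". The margin is 2 h, and 87 evaluable patients per group are required, with 90 per group to be recruited. The section does not say whether the 4 h is a total or a within-site SD.

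**The concern.** Stratifying by site in balanced blocks makes the two arms nearly equal in size within each site. A difference in mean duration between sites then largely cancels from the treatment comparison. A plain two-sample test does not use this: its pooled variance still contains the between-site component. The standard error is then larger than the true sampling variability of the estimate, and the confidence interval is wider than it needs to be.

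The direction matters. An oversized standard error makes it harder, not easier, to declare equivalence, so false claims of equivalence are not favoured. The stake is efficiency. The trial succeeds only if the whole interval lies inside ±2 h, and a wider interval spends precision that the design has already paid for.

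**Working it through.** **Inputs from the documents.** SD 4 h, margin ±2 h, α = 0.05, power 90% (written as β = 0.9), 87 per group (all E.vi).

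**Reproducing the plan's sample size.** For two one-sided 5% tests with true difference zero:

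n = 2 × [4 × (1.645 + 1.645) / 2]² = 86.6, so 87 per group.

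This matches E.vi. It also indicates that α = 0.05 applies to each one-sided test, which corresponds to a 90% confidence interval; α = 0.025 per side would give 104.

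**Assumption.** Let ρ be the share of total variance due to site. The documents give no value, so I use 0, 0.02, 0.05, 0.10 and 0.20. To put these on a clinical scale, with two equal sites and total SD 4 h the site means are 2 × 4 × √ρ = 0, 1.13, 1.79, 2.53 and 3.58 h apart. The last two exceed the trial's own margin and are large.

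**Case A: 4 h is the total SD.**

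- SE used by the unadjusted test: SE_total = 4 × √(2/87) = 0.6065 h.
- True SE under site-stratified allocation, which the adjusted model estimates: SE_true = SE_total × √(1 − ρ).
- 90% CI half-width: 1.645 × SE_total unadjusted; 1.645 × SE_true adjusted.
- Unadjusted error rate at the margin: Φ(−1.645 × SE_total / SE_true).
- Unadjusted power at true difference zero: 2Φ[(2 − 1.645 × SE_total) / SE_true] − 1.
- Adjusted power: 2Φ(2 / SE_true − 1.645) − 1.

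| ρ | Half-width unadj. / adj. (min) | Error at margin, unadj. | Power unadj. | Power adj. | Gain (points) |
|---|---|---|---|---|---|
| 0 | 59.9 / 59.9 | 5.00% | 90.16% | 90.16% | 0 |
| 0.02 | 59.9 / 59.3 | 4.83% | 90.50% | 90.83% | 0.33 |
| 0.05 | 59.9 / 58.3 | 4.57% | 91.01% | 91.79% | 0.78 |
| 0.10 | 59.9 / 56.8 | 4.15% | 91.85% | 93.29% | 1.44 |
| 0.20 | 59.9 / 53.5 | 3.30% | 93.54% | 95.89% | 2.35 |

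Unadjusted power stays above 90% throughout. It rises with ρ because the estimate itself becomes less variable; adjustment lets the interval reflect that.

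**Case B: 4 h is the within-site SD.** The true SE stays at 0.6065 h and the unadjusted SE is 0.6065 / √(1 − ρ). Unadjusted power is 2Φ[(2 − 1.645 × 0.6065 / √(1 − ρ)) / 0.6065] − 1 = 90.2, 89.8, 89.3, 88.2 and 85.5%, against 90.2% adjusted. On this reading the gap between two equal sites is 2 × 4 × √(ρ / (1 − ρ)) = 0, 1.14, 1.84, 2.67 and 4.00 h.

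**Non-zero true difference.** The figures above assume a true difference of exactly zero. In case A with ρ = 0.05, 0.10 and 0.20, the gain is 1.2, 2.4 and 4.7 points at an assumed true difference of 0.5 h, and 1.7, 3.6 and 7.7 points at 1 h.

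**Simulation check.** With t-based intervals, three equal sites, 87 per group and total SD 4 h (200,000 runs), power unadjusted / adjusted was 89.8/89.8, 90.2/90.5, 90.7/91.5, 91.5/93.0 and 93.3/95.8%. Adjusted error at the margin was 4.9 to 5.0%. The lost degrees of freedom therefore have no visible cost when sites do not differ.

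**The case against.** The strongest reply is that nothing in the plan is wrong. The unadjusted test is valid, its error rate at the margin is at or below 5%, and the stated sample size reproduces. This is correct, and the point is offered only as an improvement.

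The gain is also small unless sites differ widely. At ρ of 0.02 and 0.05 the half-width shrinks by 0.6 and 1.5 minutes out of about 60. The block technique is closely specified in E.iii, which argues against very large site differences, though it does not exclude them: operators range from staff to supervised residents, and surgical infiltration may be 10 to 40 ml with a choice of agent. The documents do not say that these vary by site. If one site recruits nearly everyone, the benefit approaches zero. All of this stands and limits the size of the point.

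The lowest power figure, 85.5%, needs both the within-site reading of the SD and two equal sites 4.0 h apart. If all 90 recruited per group are evaluable, unadjusted power on that reading is still 90.9% at ρ = 0.02 and 90.4% at 0.05, and drops below target only at 0.10 (89.5%) and 0.20 (87.0%). That is a best case, because the 3 extra patients per group are there to cover losses.

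None of this favours leaving site out. At ρ = 0 the adjusted analysis performs as well as the unadjusted one; if sites differ, it performs better.

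**Conclusion.** The concern holds as a low-cost improvement, not as an error. The mismatch between stratified allocation and an unstratified analysis is clear from the text, and so is its direction: if sites differ, the test is conservative and the interval too wide.

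The size is uncertain because it depends on a between-site variance, and on a number and balance of sites, that the documents do not give. With total SD 4 h and a true difference of zero, the power forgone is under 1 point for site shares up to 5%, and about 1.4 and 2.3 points at 10% and 20%. It is nil if sites do not differ, and larger if the true difference is not zero or if 4 h is a within-site SD. The planned sample size need not change.

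**What to change.** In E.vii, replace the plain two-sample test for the primary outcome with text such as:

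*The difference in mean duration of sensory block and its 90% confidence interval will be estimated from a linear model with treatment and site as fixed effects; equivalence is concluded if the interval lies entirely within ±2 hours.*

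Use the same model for the time-based secondary outcomes. Add site to the models for opioid consumption, NRS and blood glucose; this follows the same principle, although the figures above concern only the primary outcome. Oxygen saturation is listed in E.v without a named method in E.vii and could use the same model. Leave the chi-square or Fisher tests for paresthesia, infection and nausea as planned. Keep the unadjusted two-sample test as a sensitivity analysis, and state in advance how very small sites will be pooled.

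The change should be made before any unblinded analysis. Section E.ix states that "A single interim analysis will be performed at 50% enrolment", so it belongs before that point, and the text should say which model the interim test uses.

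The cost is a few sentences and one degree of freedom per additional site out of about 172 (174 patients less 2). No new data and no change in sample size are needed.

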**E. Methods**

**i. Inclusion Criteria/Sample population**

1. Patients undergoing arthroscopic shoulder surgery
2. ASA functional status class I to III
3. Age 18 to 80 years
4. BMI  $\leq$  35 kg/m^2

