### Data collection plan

Data will be collected according to the Source-CRFs/CRFs. All data collection will be conducted by a research staff member, either a research assistant or a co-investigator, who is blinded to the patient's treatment allocation.

1. Identifying information, exclusion criteria, surgical procedure description and anesthesia data will be collected preoperatively.
2. Procedure details, including: sedative used, procedure duration (end of injection), pain on injection and the presence of blood will be collected during the block procedure.
3. Pinprick sensation in the C4-T1 dermatomes at 10 and 20 minutes post block (to characterize presence/absence of block). Pain Sensation is characterized as a: (2) = sharp sensation, (1) = dull sensation only, or (0) = no sensation.
4. Motor function (elbow flexion for biceps) at 10 and 20 minutes post block. Power is graded using (2) = normal movement, (1) = reduced movement and (0) = no movement.
5. Intra-operative anesthesia data collection. Time of first Incision, administered anesthesia and time procedure ended.
6. Room air pulse oximetry 1 hour after admission to PACU/recovery room (to characterize respiratory function near discharge)
7. Blood Glucose level in PACU.
8. An account of analgesia administered in PACU.
9. Numerical rating scale (NRS) pain scores 1 hour after admission to PACU to PACU/recovery room
10. Information regarding post block complications (including pain and bruising around the block site) will be collected in a 1 week postoperative telephone call with the patient.
11. Time to first pain sensation in the shoulder, analgesic use and return of the affected hand to normal strength will be captured in the take home patient diary and reported at follow-up telephone calls.
12. NRS pain scores, analgesia consumption and side effects experienced will be captured at: 12hours/bed time, 24 hours and 7 days post-operatively in the patient's diary reported at follow-up telephone calls.

Upon achieving enrolment of the specified 180 patients and data is collected, the database will be verified, and analyzed by the biostatistician.

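### The primary equivalence test is valid as sized, but it leaves unused baseline data (procedure, age, gender) that could modestly sharpen the arm difference at almost no cost

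*Combined protocol and SAP*

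**What the plan says.** All references are to the combined protocol and SAP.

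- Section iv: the primary outcome is sensory block duration, "defined as time from end of injection to first sensation of pain at surgical site".
- Section vii: this outcome "will be compared between the two groups using a two sample equivalence test of means". Neither a covariate, nor a site term, nor an adjusted sensitivity analysis is named. The time-based secondary outcomes are to be handled in the same way.
- Section i: eligibility is stated as "Patients undergoing arthroscopic shoulder surgery", ages 18 to 80, with no list of operations.
- Section iii: randomization is stratified by site only.
- Data collection plan, item 1: "Identifying information, exclusion criteria, surgical procedure description and anesthesia data will be collected preoperatively".
- Section viii: the case report forms carry "patient study number, age (in years), and gender as identifiers".
- Section vi: "we expect mean sensory block duration of 12 hours with a standard deviation of 4 hours", and "Defining an equivalency margin of 2 hours" leads to 87 per group, with 90 per group to be recruited.

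**The concern.** The outcome is when the patient first feels pain from the operation. It may therefore depend on what was done to the shoulder as well as on how long the block lasts. Procedure is controlled neither in the randomization nor in the analysis. If procedure, age or sex predicts duration, the two-sample test leaves that variation in the error term.

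The margin for this is thin. With the plan's inputs, the 90% interval has a half-width of about 1.0 h, so equivalence within 2 h can be declared only if the observed difference is below about 1.0 h. Power near 90% also requires a true difference of exactly zero. By the normal approximation it is about 79% at a true difference of 0.5 h and 50% at 1 h. A narrower interval would therefore bear directly on the primary conclusion, and the data that might narrow it are already on the forms.

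**Working it through.** **Inputs from the documents.** SD 4 h, margin 2 h (taken as plus or minus 2 h), alpha 0.05, 87 per group, 1:1 allocation.

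**Readings and assumptions.**
- Alpha is taken as 0.05 for each one-sided test, and the stated beta of 0.9 is read as power 0.90.
- The true difference is taken as 0 h. The plan does not state this value, but it fits the hypothesis ("provides similar duration analgesia to that of US-ISB with local anesthetic alone and intravenous dexamethasone") and reproduces the plan's sample size.
- R-squared, the share of outcome variance explained by the covariates, is not in the documents. The range 0 to 0.20 is assumed.

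**Step 1: reproduce the plan's figure.** For two one-sided tests at zero true difference, n per group = 2 × [SD × (z₀.₉₅ + z₀.₉₅) / margin]² = 2 × [4 × (1.645 + 1.645) / 2]² = 86.6, rounded up to 87. This matches.

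**Step 2: the unadjusted test at 87 per group.** SE = 4 × √(2/87) = 0.606 h. With 172 df, t₀.₉₅ = 1.654, so the 90% interval half-width is 1.654 × 0.606 = 1.00 h. Power is 90.2% by the normal approximation and 89.9% with the t distribution. The t-based figure is the comparator below.

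**Step 3: the adjusted model.** Procedure in two groups, age and sex use k = 3 df, leaving 172 − 3 = 169. Two things change.
- The residual SD becomes 4 × √(1 − R²).
- Estimating the covariates inflates the standard error by f = √(1 + 3/168) = 1.009, the expected cost of chance covariate imbalance.

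The half-width is 1.654 × 4√(1 − R²) × √(2/87) × 1.009. Power is the probability that the estimate plus or minus this t-based half-width falls inside plus or minus 2 h, averaged over the sampling distribution of the residual SD. The equivalent unadjusted n is 87 / [f² × (1 − R²)], with f² = 1.018.

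| Assumed R² | Residual SD (h) | Half-width (h) | Power at zero difference | Equivalent n per group |
|---|---|---|---|---|
| unadjusted | 4.00 | 1.00 | 89.9% | 87 |
| 0 | 4.00 | 1.01 | 89.3% | 85 |
| 0.02 | 3.96 | 1.00 | 90.0% | 87 |
| 0.05 | 3.90 | 0.99 | 91.0% | 90 |
| 0.10 | 3.79 | 0.96 | 92.6% | 95 |
| 0.20 | 3.58 | 0.91 | 95.4% | 107 |

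**Step 4: break-even.** The adjusted SE equals the unadjusted one when f² × (1 − R²) = 1, so R² = 1 − 1/1.018, or about 0.02.

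**Step 5: adding site.** The number of sites is not given. Each site beyond the first uses one more df. With 4 df in all, power at R² 0, 0.02, 0.05, 0.10 and 0.20 is 89.1, 89.8, 90.8, 92.4 and 95.3%. With 5 df it is 88.8% at R² 0 and 92.3% at 0.10, and break-even moves to about 0.03.

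**The case against.** The strongest reply is that nothing is wrong with the plan. A randomized two-sample comparison needs no covariates to be valid, and the sample size was computed for exactly this test. That stands in full.

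The second reply is that a reader might infer that free precision is being thrown away across a broad mix of minor and painful operations. The documents do not support that. They give no R-squared, no expected case mix and no grading of operations by pain; the breadth is inferred from one unrestricted criterion. The adjustment is also not strictly free, because below an R-squared of about 0.02 it loses a little. A calculation that only shrinks the SD and uses the normal approximation overstates the gain: at R-squared 0.05 it gives 91.8% against 90.2%, a rise of 1.6 points, whereas the t-based figures give 91.0% against 89.9%, a rise of 1.1.

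A reader might also count correction of a chance imbalance in procedure mix as a second benefit. It is not one. Under randomization, such imbalance is already part of the unadjusted standard error, and removing it is the precision gain itself.

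Finally, only a procedure description is collected, so categories have to be defined and coded, and the preoperative description may differ from the operation performed. That is a real cost, but a small one. What survives is that the possible loss is small and bounded, while the possible gain is larger and needs no new data.

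**Conclusion.** The point holds as a recommended improvement, not as a fault. The plan leaves unused baseline data that may be prognostic for its primary outcome. Against 89.9% unadjusted, power at zero true difference with 87 per group would change by about −0.6, +0.1, +1.1, +2.7 and +5.5 percentage points at R-squared 0, 0.02, 0.05, 0.10 and 0.20. The half-width would move from 1.00 h to between 1.01 and 0.91 h. Only the upper end of that assumed range is a sizeable gain.

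The figures rest on the plan's SD of 4 h, a margin of plus or minus 2 h, a true difference of zero, three covariate df and an R-squared that is wholly assumed. They do not show that the trial is underpowered, that its sample size is wrong or that the planned test is biased.

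**What to change.** In section vii, prespecify the primary analysis as a linear model of sensory block duration on arm, site, planned procedure category, age and sex. Declare equivalence if the 90% confidence interval for the adjusted arm difference lies within plus or minus 2 h. Keep the unadjusted two-sample test as a sensitivity analysis.

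- **Procedure:** use two groups based on the preoperative description. Write their definitions down before any unblinding, including the interim analysis at 50% enrolment, and have the coding done blind to allocation.
- **Site:** it belongs in the same model because randomization is stratified by it.
- **Secondary outcomes:** the same model may be used for time to first opioid. Extending it to motor block duration is optional, because the argument from surgical pain does not carry over to recovery of strength.

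The cost is a sentence or two of analysis text, a short coding step, and about 0.6 points of power if the covariates turn out not to be prognostic (about 1 point if site brings the model to 5 df and also explains nothing). No extra patients or data items are needed.
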